8.7.3 Vital Signs

Descriptive statistics for vital signs (systolic and diastolic blood pressures, and pulse rate) and changes from baseline values at each scheduled visit and at the end of study will be presented.

8.7.4 Cardiac Safety – Echocardiograms

LVEF (% and Z-score) over time from echocardiograms will be summarized descriptively. Shift table for LVEF will be provided comparing baseline and post-baseline changes. Echocardiogram results will be provided in subject listing.

CTCAE severity grades for decreased ejection fraction are:

- Grade 1: Not available
- Grade 2: LVEF 50-40% or 10-19% drop from baseline
- Grade 3: LVEF 39-20% or >20% drop from baseline
- Grade 4: LVEF < 20%

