8.7.2.2 Clinical Laboratory Tests

Clinical laboratory values (in SI units) at each visit will be presented for the following laboratory parameters as listed in the following table:

Table 8.7.2: Clinical Laboratory Assessments

Chemistry	Hematology	Urinalysis
Alanine aminotransferase (ALT) ¹	Hematocrit	Appearance
Alkaline phosphatase	Hemoglobin	Color
Aspartate aminotransferase (AST) ¹	MCH concentration (MCHC)	pH
Bilirubin (total)	Mean corpuscular hemoglobin (MCH)	Specific gravity
Blood urea nitrogen (BUN)	Mean corpuscular volume (MCV)	Ketones
Chloride	Platelet count	Protein
Cholesterol (total)	Red blood cell (RBC) count	Glucose
Serum creatinine	Reticulocyte count	Bilirubin
Gamma-glutamyl transpeptidase (GGT) ¹	WBC differential	Nitrite
Serum glucose, fasting ¹	Neutrophil count (absolute and %)	Urobilinogen
Lactate dehydrogenase (LDH)	Lymphocyte count (absolute and %)	Blood
Potassium	Monocyte count (absolute and %)	Creatinine
Protein (albumin and total)	Eosinophil count (absolute and %)	
Sodium	Basophil count (absolute and %)	
	White blood cell (WBC) count	

The frequency and percentage of subjects who experience abnormal clinical laboratory results (i.e. outside of reference ranges) and/or clinically significant abnormalities will be presented.

All valid assessments will be converted into SI units. In calculating change from baseline at each scheduled visit, only subjects with non-missing values at both baseline and the individual scheduled visit are included. All available data (i.e., scheduled and unscheduled assessments) are, however, used in identifying abnormalities in shift tables. Severity for the selected clinical laboratory parameters will be graded according to Common Terminology Criteria for Adverse Events (CTCAE) version 5.0. CTCAE severity grades for selected laboratory parameters are listed in Appendix 11.

Hy's Law criteria will be applied against test results. Subjects with serum total bilirubin $>2 \times \text{ULN}$ and ALT or AST $>3 \times \text{ULN}$ will be identified and further reviewed to confirm there is no other reason to explain the lab increases before confirming Hy's law status. Results will be presented in shift tables. For Hy's Law, shift tables will be produced:

- Hy's Law negative at baseline, remaining Hy's Law negative throughout the study
- Hy's Law negative at baseline, becoming Hy's Law positive at any point during the study
- Hy's Law positive at baseline and Hy's Law negative throughout the study

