11.2 Reference Values/Severity Grades

Table 11.2.1: CTCAE Severity Grades for Selected Laboratory Parameters

Laboratory Parameter	CTCAE severity grades
Fasting serum glucose	Grade 1: <LLN – 55 mg/dL; <LLN – 3.0 mmol/L Grade 2: <55 – 40 mg/dL; <3.0 – 2.2 mmol/L Grade 3: <40 – 30 mg/dL; <2.2 – 1.7 mmol/L Grade 4: < 30 mg/dL; <1.7 mmol/L
Triglycerides	Grade 1: 150 – 300 mg/dL; 1.71 – 3.42 mmol/L Grade 2: > 300 – 500 mg/dL; > 3.42 – 5.7 mmol/L Grade 3: >500 – 1000 mg/dL; > 5.7 – 11.4 mmol/L Grade 4: >1000 mg/dL; > 11.4 mmol/L

CK	Grade 1: >ULN to 2.5 x ULN Grade 2: >2.5 x ULN to 5 x ULN Grade 3: >5 x ULN to 10 x ULN Grade 4: >10 x ULN
ALT, AST	Grade 1: >ULN to 3.0 x ULN Grade 2: >3.0 x ULN to 5.0 x ULN Grade 3: >5.0 x ULN to 20.0 x ULN Grade 4: >20.0 x ULN
GGT	Grade 1: >ULN to 2.5 x ULN Grade 2: >2.5 x ULN to 5.0 x ULN Grade 3: >5.0 x ULN to 20.0 x ULN Grade 4: >20.0 x ULN

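### The LVEF severity grades in SAP 8.7.4 are not contiguous, so a few boundary readings get no grade while a smaller fall from the same baseline is Grade 2

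*SAP*

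**What the plan says.** SAP 8.7.4 (Cardiac Safety – Echocardiograms) plans three outputs: a descriptive summary, "LVEF (% and Z-score) over time from echocardiograms will be summarized descriptively"; a shift table, "Shift table for LVEF will be provided comparing baseline and post-baseline changes"; and a subject listing of echocardiogram results. It then sets out a list labelled as CTCAE grades for decreased ejection fraction:

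- The lowest grade is left empty: "Grade 1: Not available".
- The second line joins an LVEF band and a drop band by *or*: "Grade 2: LVEF 50-40% or 10-19% drop from baseline".
- The third line is built the same way: "Grade 3: LVEF 39-20% or >20% drop from baseline".
- The last line uses LVEF alone: "Grade 4: LVEF < 20" (in per cent).

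The section names no CTCAE version. Elsewhere the SAP uses version 5.0: laboratory values are "graded according to Common Terminology Criteria for Adverse Events (CTCAE) version 5.0" (8.7.2.2), and 8.7.1 names the same version for adverse events. Protocol 8.5.2 names version 4.0 for adverse events.

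Neither document gives a rounding or tie rule for LVEF, or says whether the drop is in percentage points or relative to baseline. Protocol 7.5.2.2 leaves echocardiogram detail to the Study Reference Manual.

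**The concern.** A severity scale should place every abnormal reading in one grade, and the grade should not fall as the reading worsens. This list fails on both counts at its boundaries. The drop criterion stops at 19 and resumes above 20. The LVEF criterion stops at 40 and resumes at 39. Because Grade 1 is unavailable, a reading that misses Grades 2 to 4 has no grade.

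The programmer of the shift table must put each reading somewhere, and for these readings the SAP gives no instruction. The choice would be made without documentation, possibly after the data have been seen. A substantial fall in EF could be left out of the graded categories while a slightly smaller one is counted.

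The other graded parameters in the SAP do not have this problem. In Table 11.2.1, for example, CK has "Grade 2: >2.5 x ULN to 5 x ULN", and Grade 3 starts directly above 5 x ULN.

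**Working it through.** **Inputs.** The four grade lines of SAP 8.7.4, applied literally. Let b be baseline LVEF and v the later LVEF, both in per cent.

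- Drop in points: d = b − v. Relative drop: d = 100 × (b − v)/b.
- Grade 2 if 40 ≤ v ≤ 50 or 10 ≤ d ≤ 19.
- Grade 3 if 20 ≤ v ≤ 39 or d > 20.
- Grade 4 if v < 20.
- If more than one grade is met, the highest is taken. The SAP does not say this; it is an assumption.

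The plan states no figure to reproduce here, so the check is whether every reading receives a grade.

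**Worked pairs.**

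| b → v | Drop, points | Drop, relative | Grade, points | Grade, relative |
|---|---|---|---|---|
| 75 → 56 | 19 | 25.3% | 2 | 3 |
| 75 → 55 | 20 | 26.7% | **none** | 3 |
| 75 → 54 | 21 | 28.0% | 3 | 3 |
| 65 → 53 | 12 | 18.5% | 2 | 2 |
| 65 → 52 | 13 | 20.0% | 2 | **none** |
| 65 → 51 | 14 | 21.5% | 2 | 3 |
| 43 → 40 | 3 | 7.0% | 2 | 2 |
| 43 → 39.5 | 3.5 | 8.1% | **none** | **none** |
| 43 → 39 | 4 | 9.3% | 3 | 3 |
| 60 → 40 | 20 | 33.3% | 2 | 3 |
| 60 → 39.5 | 20.5 | 34.2% | 3 | 3 |

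The first three blocks of three show the order breaking: Grade 2, no grade, Grade 3 as v falls, under at least one reading of the drop. The last two rows show the other criterion supplying a grade.

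**When the drop gap leaves a reading ungraded.** This requires 19 < d ≤ 20 and an LVEF outside every band, so v > 50 or 39 < v < 40.

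- Points, drop of exactly 20: b − 20 > 50 gives b > 70. In whole numbers this covers every baseline from 71 to 85 (85 is an assumed upper limit). The other route is b between 59 and 60.
- Relative, drop of exactly 20%: 0.8b > 50 gives b > 62.5. The other route is 39 < 0.8b < 40, so b between 48.75 and 50.

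**When the LVEF gap leaves a reading ungraded.** Take v = 39.5.

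- Points: d < 10 gives b < 49.5; 19 < d ≤ 20 gives 58.5 < b ≤ 59.5.
- Relative: b < 39.5/0.90 = 43.9; or b above 39.5/0.81 = 48.8 and up to 39.5/0.80 = 49.4.

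**Unit of the drop.** The same pair can change grade with the reading chosen: 75 → 56 is Grade 2 in points and Grade 3 in relative terms.

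**Check of contiguous bands.** Use Grade 2 = drop of at least 10 and less than 20, or LVEF 40-50%; and Grade 3 = drop of at least 20, or LVEF 20 to less than 40%. On a half-point grid with baselines from 40 to 85, no pair with LVEF of 50 or below, or a drop of 10 or more, is left ungraded under either reading. The change also regrades some readings that already have a grade: in points, 60 → 40 moves from Grade 2 to Grade 3.

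**The case against.** The strongest reply is that very little turns on this, and most of that reply stands.

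- A reader might infer that every 20% drop, and every LVEF between 39% and 40%, goes ungraded. The text does not support that. Each grade joins two criteria by *or*, so 20-point falls from 60, 65 or 70 end at 40, 45 or 50 and are Grade 2, and 60 → 39.5 is Grade 3.
- A reader might infer that the affected readings are among the most severe. In whole numbers on the points reading, they are all still above 50% after the fall, outside the lowest graded LVEF band.
- The gap between 39 and 40 exists only if LVEF is recorded or derived with decimals, which the documents do not say.
- A reader might infer that an ungraded fall would be shown as normal. SAP 8.7.4 does not lay out the shift table, so this is unknown.
- A reader might link the gap to the primary endpoint because that endpoint counts cardiomyopathy events. SAP 5.2 defines those events by acute care, hospitalisation, emergency intervention or similar, not by LVEF grade.
- The falls remain visible. SAP 8.7.4 summarises LVEF and lists the results, and SAP 8.5.2 summarises EF and its change by visit.
- The list is labelled CTCAE, so the gaps may come from the source scale. The documents do not reproduce that scale, so neither a faithful copy nor a transcription error can be shown.

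The last point does not remove the need for a rule. Even if the source has the same gaps, the shift table needs a stated convention for the readings that fall in them. Nor would a rounding rule alone be enough, because a drop of exactly 20 is ungraded in whole numbers.

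**Conclusion.** The point holds in a narrow form. As written, the LVEF grades have gaps on both criteria, and a reading in one gap is ungraded when the other criterion is also not met. On either interpretation of the drop, a larger fall can be ungraded while a smaller one from the same baseline is Grade 2.

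It is minor: boundary readings in a descriptive safety table, with no effect on the primary analysis. The documents give no distribution of LVEF, so the number of subjects affected cannot be estimated.

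The conclusion rests on three assumptions: the shift table uses the grades listed beneath it, the limits are applied literally, and the highest grade met is assigned. The part about values between 39% and 40% also assumes decimal LVEF values.

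**What to change.** In SAP 8.7.4:

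1. Check the list against the CTCAE version the SAP names (5.0), note that the protocol names 4.0, and correct any transcription difference.
2. Make the analysis bands contiguous, so that every LVEF of 50% or below and every drop of 10 or more receives one grade that does not fall as severity rises. The bands tested above are one example; the sponsor should decide which grade takes the boundary values.
3. State whether the drop is in percentage points or relative per cent, how LVEF is rounded, and that the higher grade applies when the two criteria disagree.
4. If the resulting bands differ from CTCAE, label them as an analysis convention and not as CTCAE grades.

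The cost is a few lines of SAP text and a small programming change, with no new data. It should be done before the shift table is produced.

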8.7.5 Physical Examination

A complete physical examination is performed at the Baseline visit and at 6-month intervals (or Early Termination). Clinically significant changes from baseline to scheduled timepoints in physical examination will be reported on the adverse event CRF and thus not presented separately.

8.7.6 Pregnancy Test

Pregnancy test for females with child-bearing potential will be conducted at the scheduled study visit and the results will be provided in a listing.

9 LIST OF PLANNED TABLES, LISTINGS, AND FIGURES

List of planned tables, listings, and figures will be provided in a separate document.

11 APPENDICES

11.1 Summary of Efficacy Endpoints and Analysis

Table 11.1.1: Summary Table of UX007-CL202 Efficacy Endpoints and Analysis

Test / Instrument	Efficacy Endpoint	Analysis Population (Age criteria if applicable)	Type of Efficacy Analysis	Study Period (Visits selected if not all)	Statistical approach
MCE	Annualized event rate of MCE	Full analysis set	Primary	Period 1	Descriptive statistics
MCE	Annualized event rate of MCE by event type	Full analysis set	Secondary	Period 1	Descriptive statistics
	Annualized duration of MCE, and by event type	Full analysis set	Secondary	Period 1	Descriptive statistics
MCE	Annualized event rate of MCE and by event type; Annualized event rate of MCE and by event type;	UX007/trihep naïve subjects	Additional Efficacy Analyses	Period 1 & 3	Descriptive statistics & Comparison between pre- and post-UX007 MCE rates via paired t-test, Wilcoxon signed rank test, and NB
MCE	Annualized event rate of MCE and by event type; Annualized event rate of MCE and by event type;	UX007-CL201 rollover subjects	Integrated Analyses	Period 2 & 3	Descriptive statistics
ECHO	Change from baseline of EF, ventricle size, and SF	Full analysis set	Secondary	Period 1	Descriptive statistics
		UX007/trihep naïve subjects	Additional Efficacy Analyses	Period 1 (all visits)	Descriptive statistics & Paired t-test
		UX007-CL201 rollover subjects	Integrated Analyses	Period 2 (all visits)	Descriptive statistics

Test / Instrument	Efficacy Endpoint	Analysis Population (Age criteria if applicable)	Type of Efficacy Analysis	Study Period (Visits selected if not all)	Statistical approach
SF-12	Change from baseline –PCS, MCS, and individual domain	FAS-SF-12 (age ≥18)	Exploratory	Period 1 (all visits)	Descriptive statistics
		UX007/trihep naïve subjects in FAS-SF-12	Additional Efficacy Analysis	Period 1 (all visits)	Descriptive statistics & GEE
SF-10	Change from baseline –PHS and PSS	FAS (age ≥6 - <18)	Exploratory	Period 1	Descriptive statistics
		UX007/trihep naïve subjects in FAS-SF-10	Additional Efficacy Analysis	Period 1 (all visits)	Descriptive statistics & GEE
Clinical Biomarker	Change from baseline in serum creatine kinase, fasting serum glucose, ALT, AST, GGT	Full analysis set	Exploratory	Period 1 (all visits)	Descriptive statistics
		UX007/trihep naïve subjects	Additional Efficacy Analysis	Period 1 (all visits)	Descriptive statistics & Paired t-test
Growth Measurements	Change from baseline –Height, Weight, and head circumference (subjects ≤36 months of age only)	Full analysis set	Exploratory	Period 1	Descriptive statistics
		UX007-CL201 rollover subjects	Integrated Analyses	Period 2 (baseline, all visits)	Descriptive statistics

Note that sensitivity analyses of MCE endpoints are not included above but are summarized in Sections 8.5.4.2 and 8.5.5.2 for the Naïve Cohort and the CL201 Rollover Cohort, respectively.

11.2 Reference Values/Severity Grades

Table 11.2.1: CTCAE Severity Grades for Selected Laboratory Parameters

Laboratory Parameter	CTCAE severity grades
Fasting serum glucose	Grade 1: <LLN – 55 mg/dL; <LLN – 3.0 mmol/L Grade 2: <55 – 40 mg/dL; <3.0 – 2.2 mmol/L Grade 3: <40 – 30 mg/dL; <2.2 – 1.7 mmol/L Grade 4: < 30 mg/dL; <1.7 mmol/L
Triglycerides	Grade 1: 150 – 300 mg/dL; 1.71 – 3.42 mmol/L Grade 2: > 300 – 500 mg/dL; > 3.42 – 5.7 mmol/L Grade 3: >500 – 1000 mg/dL; > 5.7 – 11.4 mmol/L Grade 4: >1000 mg/dL; > 11.4 mmol/L

CK	Grade 1: >ULN to 2.5 x ULN Grade 2: >2.5 x ULN to 5 x ULN Grade 3: >5 x ULN to 10 x ULN Grade 4: >10 x ULN
ALT, AST	Grade 1: >ULN to 3.0 x ULN Grade 2: >3.0 x ULN to 5.0 x ULN Grade 3: >5.0 x ULN to 20.0 x ULN Grade 4: >20.0 x ULN
GGT	Grade 1: >ULN to 2.5 x ULN Grade 2: >2.5 x ULN to 5.0 x ULN Grade 3: >5.0 x ULN to 20.0 x ULN Grade 4: >20.0 x ULN

11.3 MedDRA Search Strategy for GI TEAEs and Hepatobiliary TEAEs

Adverse Events of Special Interest for ISS for UX007 LC-FAOD	MedDRA Search Strategy (version 23.1)
Gastrointestinal Disorders	Gastrointestinal Disorders SOC (all Preferred Terms)
Hepatobiliary Disorders	See table below

MedDRA search strategies for all AESIs are based on MedDRA version 23.1.

Table 11.3.1: Hepatobiliary Disorders

Hepatobiliary Disorders	System Organ Class	Preferred Term
	Hepatobiliary Disorders	Bile duct stenosis
	Hepatobiliary Disorders	Bile duct obstruction
	Hepatobiliary Disorders	Bile duct stone
	Hepatobiliary Disorders	Obstructive pancreatitis
	Hepatobiliary Disorders	Pancreatitis acute
	Hepatobiliary Disorders	Pancreatitis chronic
	Hepatobiliary Disorders	Pancreatitis relapsing
	Hepatobiliary Disorders	Cholecystitis
	Hepatobiliary Disorders	Cholecystitis acute
	Hepatobiliary Disorders	Cholecystitis chronic

Hepatobiliary Disorders	System Organ Class	Preferred Term
	Hepatobiliary Disorders	Cholelithiasis
	Hepatobiliary Disorders	Cholelithiasis obstructive
	Hepatobiliary Disorders	Pseudocholelithiasis
	Hepatobiliary Disorders	Gallbladder enlargement
	Hepatobiliary Disorders	Gallbladder obstruction
	Hepatobiliary Disorders	Hepatic failure
	Hepatobiliary Disorders	Acute hepatic failure
	Hepatobiliary Disorders	Subacute hepatic failure
	Hepatobiliary Disorders	Acute on Chronic hepatic failure
	Hepatobiliary Disorders	Chronic hepatic failure
	Hepatobiliary Disorders	Drug-induced liver injury
	Hepatobiliary Disorders	Mixed liver injury
	Hepatobiliary Disorders	Cholestasis
	Hepatobiliary Disorders	Hepatitis cholestatic
	Hepatobiliary Disorders	Jaundice
	Hepatobiliary Disorders	Jaundice cholestatic
	Hepatobiliary Disorders	Icterus
	Hepatobiliary Disorders	Ocular icterus
	Hepatobiliary Disorders	Ascites
	Hepatobiliary Disorders	Biliary ascites
	Hepatobiliary Disorders	Hepatic congestion
	Hepatobiliary Disorders	Hepatomegaly
	Hepatobiliary Disorders	Hepatosplenomegaly
	Hepatobiliary Disorders	Hepatic liver injury
	Hepatobiliary Disorders	Hepatic steato-fibrosis
	Hepatobiliary Disorders	Hepatic steatosis
	Hepatobiliary Disorders	Hepatocellular injury
	Hepatobiliary Disorders	Liver injury
	Hepatobiliary Disorders	Non-alcoholic fatty liver
	Hepatobiliary Disorders	Non-alcoholic steatohepatitis
	Hepatobiliary Disorders	Steatohepatitis
	Investigations	Alanine aminotransferase abnormal
	Investigations	Alanine aminotransferase increased
	Investigations	Aspartate aminotransferase abnormal
	Investigations	Aspartate aminotransferase increased
	Investigations	Blood bilirubin abnormal
	Investigations	Blood bilirubin increased
	Investigations	Bilirubin conjugated abnormal
	Investigations	Bilirubin conjugated increased
	Investigations	Gamma-glutamyltransferase abnormal
	Investigations	Gamma-glutamyltransferase increased
	Investigations	Hepatic enzyme abnormal
	Investigations	Hepatic enzyme increased
	Investigations	Transaminases abnormal
	Investigations	Transaminases increased
	Investigations	Amylase abnormal

Hepatobiliary Disorders	System Organ Class	Preferred Term
	Investigations	Blood amylase abnormal
	Investigations	Amylase increased
	Investigations	Blood amylase increased
	Investigations	Lipase abnormal
	Investigations	Lipase increased
	Investigations	Alkaline phosphatase abnormal
	Investigations	Blood alkaline phosphatase increased

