5.4 Study Rationale

LC-FAOD are caused by defects in the metabolic pathway that converts fatty acids into energy, leading to deficiencies in energy metabolism. The metabolic deficiency can deplete energy sources, resulting in serious clinical manifestations including hypotonia, rhabdomyolysis, liver dysfunction and hypoglycemia, and cardiomyopathy. These LC-FAOD major events are not sufficiently controlled in many patients by current standard of care, usually consisting of avoidance of fasting, low-fat/high-carbohydrate diet, dietary medium chain triglycerides (MCT oil), and/or carnitine supplementation. MCT oil, an even chain fatty acid, can provide medium chain fatty acids that bypass the specific LC-FAOD pathway defects but may not restore energy metabolism fully. In addition to supplying medium chain fatty acids, UX007 (triheptanoin), a specialized medium odd-chain (C7) triglyceride, also replaces deficient mitochondrial TCA cycle intermediates via the generation of 3-carbon intermediates, thereby improving energy metabolism.

At the time of protocol development, triheptanoin had been studied in many types of LC-FAOD for more than 13 years. Published reports describe profound clinical responses to triheptanoin, including improved physical capacity and a reduction of frequency and severity of major LC-FAOD events (rhabdomyolysis, hypoglycemia, liver function and hepatomegaly, and cardiomyopathy). Numerous LC-FAOD patients have participated, or are actively participating in multiple clinical studies or treatment programs with UX007/triheptanoin conducted by various sponsors and investigational sites.

This open-label long-term safety and efficacy extension study will provide an opportunity for LC-FAOD patients to be treated with UX007 for up to 7 years or until commercial availability of UX007 in any region, whichever occurs first, under a single standardized protocol. The subjects may have participated in other studies or treatment programs with UX007/triheptanoin or be treatment naïve and have clear unmet need but would be consolidated into one program for long-term maintenance and consistent safety monitoring. The study is designed to obtain long-term safety and efficacy information and evaluate maintenance of efficacy in a diverse LC-FAOD population.

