8.7.1 Adverse Events

Adverse events will be coded by system organ class and preferred term using the Medical Dictionary for Regulatory Activities (MedDRA version 23.1). The severity of an AE will be based on Common Terminology Criteria for Adverse Events (CTCAE), Version 5.0. If an AE cannot be graded based on CTCAE, the investigator will assign a severity based on 1 = mild, 2 = moderate, 3 = severe, 4 = life threatening, and 5 = Death.

An AE (classified by preferred term) will be considered a treatment emergent adverse event (TEAE) if it occurred on or after the first dose of UX007 and was not present prior to the first dose or worsening in severity or frequency of a preexisting condition. AEs that started in UX007-CL201 and continued into UX007-CL202 will not be considered UX007-CL202 TEAE since the start date is prior to UX007-CL202 first dose.

The following subject incidence of AEs will be summarized:

- Summary of TEAEs
- TEAEs by SOC and PT (preferred term)
- Related TEAEs by SOC and PT
- Serious TEAEs by SOC and PT
- Serious Related TEAEs by SOC and PT
- Grade 3 or 4 TEAEs by SOC and PT
- Deaths by SOC and PT
- TEAEs leading to discontinuation of study treatment by SOC and PT
- TEAEs by PT
- TEAEs leading to dose reduction by SOC and PT
- TEAEs leading to treatment interruption by SOC and PT
- TEAEs by PT
- TEAEs in the GI SOC
- Related TEAEs in the GI SOC
- GI ADRs
- GI ADRs leading to treatment discontinuation

Hepatobiliary TEAEs (see Appendix 11.4) For those AEs that occurred more than once during the study, the maximum severity or highest grade causality will be used to summarize the subject incidence. Exposure-adjusted adverse event incidence rates will also be presented at the preferred term level.

The number and percent of subjects experiencing one or more TEAE by SOC and PT in order of descending frequency may be summarized by age, gender and subtype of FAOD

history depending on the sample size. The planned age categories are ‘0-1 year’, ‘>1-6 years’, ‘>6-18 years’ and ‘>18 years’ and some may be combined if their number of subjects is small.

In the overall summary of adverse events table, there will be separate summaries for Grade 3 and Grade 4 TEAEs.

Detailed subject listings for all AEs, serious TEAEs, AEs leading to the discontinuation of study, AEs leading to the discontinuation of treatment, and death TEAEs leading to dose reduction, and TEAEs leading to treatment interruption will also be generated.

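### The closed 63-term list for hepatobiliary TEAEs omits plain *Hepatitis*, plain *Pancreatitis* and any abnormal-liver-function term, and includes 10 pancreatic terms without rationale, so the grouped incidence can be under- or over-counted (minor)

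*SAP*

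**What the plan says.** SAP 11.3 sets out two search rules under the heading "Adverse Events of Special Interest for ISS for UX007 LC-FAOD", both on MedDRA 23.1. Gastrointestinal events are found by "Gastrointestinal Disorders SOC (all Preferred Terms", that is, by the whole system organ class. For hepatobiliary events the entry reads only "See table below", which leads to Table 11.3.1. That table is a fixed list of preferred terms filed under two classes, Hepatobiliary Disorders and Investigations. It has no SOC-wide clause, no standardised query and no wording that leaves the list open.

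Among the entries are "Hepatitis cholestatic", "Pancreatitis relapsing" and "Lipase increased".

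SAP 8.7.1 uses the list for one output, a subject-incidence summary that it introduces as "Hepatobiliary TEAEs (see Appendix 11.4". Appendix 11.4 is the visit-window table; the terms are in 11.3.

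**The concern.** A grouped special-interest summary answers a question that the term-by-term tables cannot: how many subjects had at least one event of this kind. One subject can have several terms across two organ classes, so the count cannot be rebuilt by adding rows of the SOC/PT table. Its value depends on the list that defines it.

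The list has faults in both directions. Some plain general terms are absent although their subtypes are present, so a subject coded to the plain term drops out of the group. Pancreatic terms sit under a hepatobiliary label with no stated reason, so a subject with no liver or biliary event can enter it.

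General liver events are foreseeable here. Protocol 5.4 describes the disease as causing "serious clinical manifestations including hypotonia, rhabdomyolysis, liver dysfunction and hypoglycemia, and cardiomyopathy". Protocol 7.5.5.7 has clinically significant laboratory changes recorded as adverse events where appropriate. A reader of the study report would take the hepatobiliary row at face value.

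**Working it through.** The SAP states no total for the list, so there is no plan figure to reproduce. The check is a direct count of Table 11.3.1 and a match of terms within it.

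**Size of the list**
- Hepatobiliary Disorders: 41 terms. Investigations: 22 terms. 41 + 22 = 63, all distinct.

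**Pancreatic terms**
- Under Hepatobiliary Disorders: 4 (obstructive, acute, chronic and relapsing pancreatitis).
- Under Investigations: 4 amylase and 2 lipase.
- 4 + 4 + 2 = 10, and 10/63 = 15.9% of the terms. This is a share of terms, not of events.
- Without them: 41 − 4 = 37 and 22 − 6 = 16, and 37 + 16 = 53. The 16 remaining Investigations terms are all liver tests.

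**Does the list normally carry the general term with its subtypes?**

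| Family | Plain term listed? | Subtype listed? |
|---|---|---|
| Cholecystitis | yes | yes |
| Cholelithiasis | yes | yes |
| Hepatic failure | yes | yes |
| Jaundice | yes | yes |
| Icterus | yes | yes |
| Ascites | yes | yes |
| Liver injury | yes | yes |
| Steatohepatitis | yes | yes |
| Hepatitis | **no** | yes (cholestatic) |
| Pancreatitis | **no** | yes (four) |

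Eight families follow the pattern and two break it. For pancreatitis the list is inconsistent on either reading. If pancreatic events belong in the group, the plain term is missing; if they do not, ten terms should go.

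**Abnormal liver function**
- No term in the list contains the word function. General laboratory terms are present (hepatic enzyme and transaminases, each abnormal and increased), so this gap concerns function terms and not liver tests as a whole.

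**Effect of following the rule exactly**
- Subject coded only to *Hepatitis*: not listed, not counted.
- Subject coded only to "Lipase increased": listed, counted as hepatobiliary.

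**Scale**
- One subject as a share of the planned sample is 100/N percentage points.
- Protocol 7.3 and 7.6.6, about 150 subjects: 100/150 = 0.67 points.
- SAP 3.1 and 3.6, about 100 subjects: 100/100 = 1.0 point.
- Omitted terms can only lower the count and pancreatic terms can only raise it. The documents report no events, so the net effect cannot be computed.

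**The case against.** The case for leaving the list alone has real weight.

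- **Liver safety does not rest on this row.** SAP 8.7.1 tabulates every TEAE by SOC and PT, with related, serious and Grade 3 or 4 versions and exposure-adjusted rates by preferred term. SAP 8.7.2 adds ALT, AST and GGT shift tables, incidence of abnormal laboratory results, Hy's Law shift tables and a listing, and a liver/muscle screen, all independent of how events are coded. This stands, and it is why the point is minor. These displays do not supply the grouped subject count.
- **The group carries no inference.** It is descriptive, with no test or alpha, and is not among the protocol's named safety endpoints. Its heading ties it to the ISS. This also stands, although 8.7.1 does use the list in this study.
- **The pancreatic grouping may be deliberate.** It may be, but the SAP does not say so, and the label and the missing plain term do not fit that reading. Amylase and lipase are not in the scheduled laboratory panel (Protocol Table 7.5.5.5.1), so any over-count from them may be small.
- **Liver dysfunction in Protocol 5.4 is a disease manifestation, not an adverse event category.** This is correct. The hepatic major clinical event is defined through hypoglycemia. The passage shows that liver events are foreseeable, not that the protocol requires this grouping.

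A reader might go further and infer that the list leaves out general terms throughout, that it ignores liver tests, or that the incidence will be wrong. The documents support none of these. Eight families include the general term, 16 liver-test terms are listed, and no event counts show an error in either direction. Nor do they show which terms coders use most often.

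**Conclusion.** The point holds as an internal inconsistency in Table 11.3.1 that can affect one descriptive count. The list is closed, breaks its own pattern for hepatitis and pancreatitis, has no abnormal-liver-function term, and places 10 pancreatic terms under a hepatobiliary label without explanation. The grouped incidence in SAP 8.7.1 can therefore be too low or too high. The most that can be said about size is 0.67 points per affected subject at 150 subjects, or 1.0 point at 100.

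This assumes that the table is complete as it reads, that it is applied by exact term match, and that the number treated is close to the planned number. SAP 8.5 presents analyses by cohort unless otherwise specified. Within a cohort one subject would weigh more, but the documents give no cohort sizes. How MedDRA 23.1 itself classifies these terms was not checked and is not part of the argument.

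Severity: minor.

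**What to change.** 1. In SAP 11.3, define hepatobiliary TEAEs as all preferred terms in the Hepatobiliary Disorders SOC, explicitly excluding pancreatitis terms, plus the 16 listed non-pancreatic Investigations terms and any abnormal-liver-function terms in MedDRA 23.1. The exclusion is needed because the table's own class column files pancreatitis under Hepatobiliary Disorders, so an SOC-wide rule alone would bring it back in. Confirm in MedDRA 23.1 that plain *Hepatitis* is captured; if it is not, add it by name.
2. Report the 10 pancreatic terms together with plain *Pancreatitis* in a separate row. If the combined grouping is intended, relabel it hepatobiliary/pancreatic, add the plain term and state the reason.
3. In SAP 8.7.1, change the reference from Appendix 11.4 to Appendix 11.3.

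The cost is a short wording change and slight reprogramming on adverse events that are already coded; no new data are needed. The reported count may rise or fall. If the same list serves the ISS, make the change in both places or explain the difference.
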